6.13.5 Safety set (SAF)

The SAF includes all patients who received at least one dose of MOR00208 or LEN and had at least one post-baseline safety assessment.

A valid safety assessment includes death. A “no adverse event” record is also considered as a valid safety assessment.

Analyses using the SAF will be based on the treatment study drug actually received.

6.13.6 PK analysis set (PKAS)

The PKAS will include all patients who received at least one dose of MOR00208 and have at least one quantifiable serum MOR00208 concentration (PK parameters will be calculated as data permits).

6.13.7 Immunogenicity analysis set (IAS)

The IAS includes all patients who have at least one anti-MOR00208 antibody assessment.

6.13.8 Planned analyses for the different populations

The number of patients in each analysis set will be summarized.

Table 2 gives an overview of the assessments performed on the different analysis sets.

Table 2: Overview of the analyses performed on the different analysis populations

Analysis	All patients screened	FAS	PPS	SAF	PKAS	IAS
Patient disposition	x					
Summary of baseline characteristics		x		x		
Overall response rate, disease control rate (central and local evaluation)		x	x			
PFS (central and local evaluation)		x	x			
Duration of response, duration of best overall response (central and local evaluation)		x	x			
Time to response (central and local evaluation)		x	x			

STATISTICAL ANALYSIS PLAN

 MorphoSys AG
 MOR208C203

Time to next treatment		x	x			
Time to progression (central and local evaluation)		x	x			
Overall survival		x	x			
Efficacy subgroup analyses		x	x			
ECOG performance status, B-symptoms		x		x		
Summary of drug exposure and compliance		x		x		
Summary of prior therapies		x		x		
Summary of pre-medication, prior medication, concomitant medication		x		x		
Summary of medical history and current medical condition		x		x		
Summary of vital signs, 12-lead ECG, laboratory safety evaluations, adverse events				x		
Pharmacokinetic analyses					x	
Immunogenicity analyses						x
Descriptive biomarker analyses		x				

6.13.9 Withdrawal of informed consent

Any data collected in the clinical database after a patient withdraws informed consent from all further participation in the trial, will not be included in the analysis data sets. The date on which a patient withdraws full consent is recorded in the eCRF (on the end of treatment eCRF page). Note: Patients who withdraw consent from treatment but consent to post-treatment follow up and/or survival follow up are not considered as having withdrawn full consent and no such withdrawal of consent date is recorded in the eCRF. Such post-treatment assessments will be included in the analysis data sets.

Any data that is entered in the clinical database without the consent of the patient will be excluded from the analysis sets. Only exceptions are the information entered to close a page after the date of withdrawal of consent e.g. End of Treatment, End of post-treatment follow-up.

For OS, death events in some countries can be reported if the death event can be confirmed to be captured from public records. If confirmed, the events will be included in the analysis data sets.

Third party data, e.g. PK, biomarker etc., collected in the clinical database without having obtained consent for collection will not be included in the analysis data sets. Data from such samples if collected prior to the date of consent withdrawal will be included in the analysis unless specific request is made by the patient not to analyze the sample. These data will be excluded by the presence of the appropriate protocol deviation criterion.

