5.3 Study Duration

5.3.1 Study Conduct

The study duration per patient will be at least 5 years including periods of screening (up to 28 days from signature of the Informed Consent Form (ICF), the treatment period (maximum 12 cycles for LEN + MOR00208 followed by MOR00208 monotherapy thereafter) and the survival follow-up phase. MOR00208 can be administered until disease progression as described in [Section 5.1.2](#).

The survival follow-up phase begins with the End of Treatment (EOT) Visit ([Section 7.2.2](#)). Patients will have an on-site safety evaluation visit 30-days after last administration of study treatment (LEN + MOR208 combination or either LEN or MOR208 if one of these two drugs was discontinued earlier) (30-Day Follow-up Visit). All patients discontinued for any reason other than withdrawal of consent, or death, will be contacted every 90 days by phone from the date of the 30-Day (Safety) Follow-up Visit until end of study, or until withdrawal of consent, or death, whichever comes first.

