10.6.2.2 Duration of Response (DoR) and Time to Next Treatment (TTNT)

DoR is defined as the time interval between the initial time point of tumour response (CR or PR whichever status is recorded first) and the first date that recurrence of progressive disease is documented. Response duration by the local and central assessment will be tabulated with descriptive statistics.

Disease progression is defined as the first occurrence of progressive disease according to the revised response criteria ([Cheson et al., 2007](#)) as assessed by central radiology / clinical readers.

TTNT is defined as the time from study entry (= first dosing) to the institution of next therapy for any reason including disease progression, treatment toxicity and patient preference. TTNT will be descriptively analysed.

10.6.2.3 Time to Event Variables: Progression-Free Survival (PFS), Overall Survival (OS), and Time to Progression (TTP)

PFS is defined as the time elapsed between study entry (= first dosing) and lymphoma progression or death from any cause, whichever occurs first. Patients not experiencing a lymphoma progression or death from any cause will be censored at the last available tumour assessment. The same holds true for patients who are lost-to-follow-up.

OS is defined as time from study entry (= first dosing) until the date of death from any cause. Patients who are alive but have dropped out early will be censored at the time of the last available study visit assessment.

TTP is defined as the time from study entry (= first dosing) until documented lymphoma progression or death as a result of lymphoma. The events of interest are only disease progression and death from lymphoma. Death from other causes will not be taken into account (will be censored) in the TTP evaluation. Patients not experiencing progressive disease will be censored at the last NHL assessment. Deaths from other causes will be censored at the time of death. Early drop-outs without any documented date of progression will be censored at the time of the last NHL assessment.

Kaplan-Meier methodology will be used to evaluate median survival, presenting corresponding statistical parameters and Kaplan-Meier survival curves. Further analyses concerning influence of IPI and GC/non-GC B-cells will be specified in the SAP.

TTP will be compared to the TTP of the patients' most recent therapy by tabulating descriptive statistics (including 95% confidence limits).

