6.10 Date of last contact

The date of last contact is derived for patients not known to have died at the analysis cut-off date (see section 7.4) based on the latest date among the following:

- Actual assessment dates (Labs, vital signs, performance status, tumour imaging, EOT completion, PK sample collection dates).
- Antineoplastic therapies administered after study drug discontinuation.
- Adverse events dates.
- “Date of contact” or “Last known date patient alive” collected on the “Survival Follow-up” eCRF page (if applicable).
- Date of study completion or discontinuation from the “End of Survival Follow-up” eCRF page.
- Study treatment start/end date.

The date of last contact is defined as the latest date from the above list or the cut-off date whichever comes first. In case that a date is only partially complete the following rules will be applied. If month and year are present and only the day is missing the first day of the month will be used to impute the missing date. If day and month or year is missing the date will not be imputed. The date of last contact is used for censoring of patients in the analysis of overall survival and time to next treatment.

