7.4 Data included in the analysis and cut-off date

All the analyses mentioned in Sections 8 to 16 will be performed using data collected in the database up to the data cut-off date. A cut-off date will be defined for each of these analyses and will be specified in the outputs.

Of all the termination dates of the patients included in the final analysis, the last termination visit date will be defined as the cut-off date and will be specified in the outputs.

Analyses will be based on the data collected for patients who did not fail screening, and for all patients treated prior to or on the cut-off date.

Any data collected beyond the cut-off date will not be included in the analysis. Only data with an assessment date or event start date (e.g. vital sign assessment date or start date of an adverse event) prior to or on the cut-off date will be included in the analysis. For example, if the cut-off date is 15JUN2017 then an AE starting on 13JUN2017 will be reported, whereas an AE with start date on 17JUN2017 will not be reported.

All events with an event start date either before or on the cut-off date and an event end date after the cut-off date will be reported as "continuing at the cut-off date". The same rule will be applied to events starting either before or on the cut-off date and not having a documented end date. This approach applies, in particular, to adverse event and concomitant medication reports. For these events, the end date will not be imputed and therefore will appear as missing in listings.

If it is required to impute an end date to be able to perform a specific analysis (e.g. end date after the cut-off date) the cut-off date needs to be imputed as an end date. The imputed date will be displayed and flagged in the listings.

Any data collected beyond a patient's withdrawal of consent will not be included in the analysis; except for SAEs and the date of death provided confirmed by a public registry and patient status entered after the date of withdrawal of consent e.g. end of treatment, end of post-treatment follow-up.

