10.4.3 Censoring rules and imputation

Patients who are alive or who drop out early for any reason will be censored at date of last contact.

If for a patient's death month and year are provided but the day is missing, the day will set to the first day of the month, unless other qualifying study data support survival until a later date during the same month. If day and month or year is missing, no imputation will be done and the date of death will be censored at the date of last contact. A listing showing the information on eCRF pages for survival follow-up and end of survival follow-up will be presented (for the SAF).

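### After full consent withdrawal, OS counts deaths found in public records but gives no survival time to those not found dead, so follow-up depends on the outcome; SAP 6.13.9 and 7.4 also conflict on later SAEs

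*SAP*

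**What the plan says.** SAP 6.13.9 removes data collected after a patient withdraws consent to all further participation. Patients who only stop treatment and accept follow-up are not covered. On what may still be used it says: "Only exceptions are the information entered to close a page after the date of withdrawal of consent". It then adds a rule for OS: "For OS, death events in some countries can be reported if the death event can be confirmed to be captured from public records", and "If confirmed, the events will be included in the analysis data sets".

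SAP 10.4.3 sets the censoring rule: "Patients who are alive or who drop out early for any reason will be censored at date of last contact". SAP 6.10 builds that date from study records, and for a limited group: "The date of last contact is derived for patients not known to have died at the analysis cut-off date". Under Protocol 5.3.1 the 90-day survival calls run "until end of study, or until withdrawal of consent, or death, whichever comes first", so the study itself adds no contact after withdrawal. The protocol's own OS rule (10.6.2.3) has no public-record provision: "Patients who are alive but have dropped out early will be censored at the time of the last available study visit assessment".

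SAP 7.4 also excludes data after withdrawal, but with a different list of exceptions: "except for SAEs and the date of death provided confirmed by a public registry", together with patient status entered later. Its examples of patient status are page-closing items.

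**The concern.** Take two patients who withdraw on the same day in a country where records can be checked. One dies later, the record is found, and that patient stays in the risk set until death. The other is alive at the cut-off and leaves the risk set at about the withdrawal date. Which of them stays depends on the event being measured. Kaplan-Meier requires that leaving the risk set carry no information about later death.

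OS is secondary objective 4. With no control arm, it will be read against earlier treatments. The same dates feed the follow-up summary (SAP 8.3.2), the reverse Kaplan-Meier follow-up (10.4.4) and the 24-, 30- and 48-month OS forest plots. The rule works only in some countries, while SAP 20.7.2 reports OS for US and European sites separately, so ascertainment alone could produce a regional difference. SAP 20.4.1 and 21.1 list withdrawal of consent among the OS censoring reasons, so such patients are expected.

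The SAE conflict is separate. The treatment-emergent window runs to 30 days after the last dose, and longer for related events. An SAE after withdrawal but inside that window is in or out of the SAE tables depending on which section is programmed.

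**Working it through.** **Text.** The rules, side by side, for a patient who has withdrawn full consent:

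| Situation | SAP 6.13.9 | SAP 7.4 | OS result |
|---|---|---|---|
| Death confirmed in public records | kept | kept | event at date of death |
| Not found dead | no alive date defined | no alive date defined | censored at last contact (10.4.3, 6.10) |
| SAE after withdrawal | not among the exceptions | kept | not applicable |

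**Mechanism.** An invented pair: both patients withdraw at month 6, one dies at month 18, the other is alive at a month-24 cut-off. Under the SAP rule the time observed after withdrawal is (18 − 6) + 0 = 12 months with 1 death. With both followed it is (18 − 6) + (24 − 6) = 30 months with 1 death. The death is the same, but the denominator is 12 instead of 30.

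**Size.** The plan states no OS figure to reproduce, so size comes from a simulation of 400,000 patients per scenario.
- From the documents: primary analysis about 12 months after last enrolment (SAP 5.4.2); median OS of 10.7 months in a cited lenalidomide-rituximab study (Protocol 1.3.3).
- Assumed: 18-month accrual (12 to 30 months of follow-up); medians of 24 and 36 months; exponential OS, S(t) = 2^(−t/median); 10% assigned a withdrawal time uniform over months 0 to 12, independent of prognosis; 50% or 100% searchable. At a median of 24 months about 8.5% withdraw before death, or 0.085 × 80 ≈ 7 patients.

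24-month OS, %:

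| Median (months) | True | SAP rule, half searchable | SAP rule, all searchable | Symmetric search, all searchable |
|---|---|---|---|---|
| 10.7 | 21.1 | 20.3 | 19.5 | 21.0 |
| 24 | 50.0 | 49.1 | 47.8 | 50.0 |
| 36 | 63.0 | 61.9 | 60.9 | 62.9 |

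Errors are −0.8 to −1.1 points with half searchable and −1.6 to −2.2 with all. At a median of 24 months with all searchable, estimated median OS is 22.6 instead of 24.0 months. The range runs from about half a point (5% withdrawing, half searchable) to 4.7 points (20%, all searchable, median 24). With five years of follow-up and 20% withdrawing, the largest errors are 2.0 points at 24 months and 3.7 at 48 months.

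**Dropping independence.** The death hazard after withdrawal is now multiplied by an assumed hazard ratio (HR): 10% withdrawing, half searchable, 20-month accrual, cut-off 12 months after last enrolment. Errors in 24-month OS, in points, for medians of 18 / 30 months:

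| HR after withdrawal | SAP rule | Censor all at withdrawal |
|---|---|---|
| 1 | −1.0 / −1.0 | +0.1 / 0.0 |
| 1.5 | −0.1 / −0.2 | +1.2 / +1.2 |
| 2 | +0.4 / +0.1 | +2.0 / +1.8 |
| 3 | +1.1 / +1.0 | +3.0 / +3.2 |

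A repeat run put the SAP rule at about −0.3 for an HR of 1.5. With all searchable and an HR of 2, the SAP rule gives −1.0 / −1.4 and censoring at withdrawal gives +2.1 / +2.0.

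**The case against.** The strongest objection concerns direction. A reader might infer that the rule makes OS too low. The documents do not support that as a fact: it follows only if withdrawal is independent of prognosis, and nothing in the plan says so. If sicker patients withdraw, ordinary censoring at withdrawal pushes OS up, and with partial searching the two errors can cancel or reverse, as the second table shows. This stands.

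Scale is the next objection. The rule applies in some countries only, so the all-searchable figures are an upper case. The 10% drop-out in SAP 5.3 is a sample-size allowance for ORR, not a withdrawal rate. With 80 patients the sampling standard error of 24-month OS in these simulations is about 6.3 to 6.5 points, well above the 1 to 2 points at issue. This also stands.

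Third, an alive date might enter by another route: SAP 6.10 accepts a last-known-alive date from the survival follow-up page, and 7.4 keeps patient status entered after withdrawal. But 7.4 illustrates patient status only with page-closing items, and neither section defines a date for a patient checked and not found dead. The sponsor may intend one; the SAP does not say so.

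A reader might also infer that many SAEs are at stake because patients withdraw for toxicity. The documents give no reasons for withdrawal and no counts. The SAE point is a contradiction of unknown size.

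**Conclusion.** The defect in the rule is established by the text: after full withdrawal, time at risk for OS depends on whether the patient later dies and in which country. Its effect is probably modest. Assuming 10% withdraw independently of prognosis, 24-month OS at the primary analysis is about 1 point too low with half searchable and 2 points with all. With post-withdrawal hazard ratios of 1.5 to 3 and half searchable, the error is about −0.3 to +1.1 points, so no net direction can be claimed. It is zero if nobody withdraws or no deaths are found in records. No formal test is planned for OS, and the primary ORR is not touched.

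Censoring everyone at withdrawal might look like the safe repair. It is accurate only under independence. Otherwise it discards confirmed deaths and overstates OS by about 1 to 3 points in the cases run, the flattering direction for a single-arm trial.

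The SAE conflict between 6.13.9 and 7.4 needs no assumption.

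**What to change.** 1. In SAP 6.13.9 and 10.4.3, use public records symmetrically. Where a search is allowed, check every withdrawn patient at the data cut-off. A death found is an event at the date of death. A patient not found dead is censored at the search date, capped at the cut-off. Where no search is allowed, censor at last contact before withdrawal. Add the search date to the sources in 6.10.
2. Show OS with all withdrawn patients censored at withdrawal as a sensitivity analysis, not as the main rule. Report how many withdrew and how many could be searched.
3. Put one identical list of exceptions in 6.13.9 and 7.4, retaining SAEs within the treatment-emergent window where the law permits.

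The cost is SAP wording, one date per searched patient and one extra OS run. The symmetric rule is unbiased when all withdrawn patients can be searched. It cannot repair informative withdrawal where searches are not allowed, and the report should say so.

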6.14 Efficacy Assessments

6.14.1 Response criteria

The efficacy variables / endpoints will be evaluated through central review by an Independent Radiology/Clinical Review Committee (IRC) that will apply the revised response assessment criteria based on the guidelines of the IWG reported by Cheson et al. (2007) (see **Error! Reference source not found.**). The review process will be defined in the IRC Charter.

Local assessment of efficacy response (Cheson criteria) will be required in addition to central review at the beginning of Cycle 3, Cycle 5, Cycle 7, and Cycle 10, at the end of Cycle 12 (for decisions concerning the additional Cycle 13 through Cycle 24 MOR00208 treatment) and at the EOT Visit (to determine whether the disease has progressed). During the treatment phase from Cycle 13 onwards (MOR00208 monotherapy phase) tumour response assessments will be performed as follows: for Cycles 13 - 24 local assessments of response will be done approximately every 3 months \pm 2 days from the previous scan. First assessment during this phase can be done directly 3 months after Cycle 12 Day 28 PET/CT assessment. Thus, the first response assessment after Cycle 12 is not needed at Cycle 13 Day 1. Moreover, the first assessment during the MOR00208 monotherapy phase can generally happen later than 3 months after the Cycle 12 Day 28 assessment. From Cycle 25 onwards local assessments of response will be performed approximately once per year \pm 2 weeks from the previous scan. Efficacy will be evaluated in terms of (best) ORR (primary endpoint), DCR, DoR, PFS, OS, TTP and TTNT (secondary endpoints) based on both INV and IRC response assessment. For definitions, see Sections 9 (primary endpoint) and 10 (secondary endpoints).

Table 3: Definition of Response Criteria (Cheson et al., 2007)

Response	Definition	Nodal masses	Spleen, liver	Bone marrow
CR	Disappearance of all evidence of disease	a) FDG-avid or PET positive prior to therapy; mass of any size permitted if PET negative b) Variable FDG-avid or PET negative; regression to normal size on CT	Not palpable, nodules disappeared	Infiltrate cleared on repeat biopsy; if indeterminate by morphology, immunohistochemistry should be negative
PR	Regression of measurable disease and no new sites	\geq 50% decrease in SPD of up to 6 largest dominant masses; no increase in size on CT a) FDG-avid or PET positive	\geq 50% decrease in SPD of nodules (for single nodule in greatest	Irrelevant if positive prior to therapy; cell type should be specified

STATISTICAL ANALYSIS PLAN

 MorphoSys AG
 MOR208C203

		prior to therapy; one or more PET positive at previously involved site b) Variable FDG-avid or PET negative; regression on CT	transverse diameter); no increase in size of liver or spleen	
SD	Failure to attain CR/PR or PD	a) FDG-avid or PET positive prior to therapy; PET positive at prior sites of disease and no new sites on CT or PET b) Variable FDG-avid or PET negative; no change in size of previous lesions on CT		
Relapsed disease or PD	Any new lesion or increase by $\geq 50\%$ of previously involved sites from nadir	a) Appearance of a new lesion(s) >1.5 cm in any axis, $\geq 50\%$ increase in SPD of more than one node, or $\geq 50\%$ increase in longest diameter of a previously identified node >1 cm in short axis b) Lesions PET positive if FDG-avid lymphoma or PET positive prior to therapy	$>50\%$ increase from nadir in the SPD of any previous lesions	New or recurrent involvement

Abbreviations: CR = complete response; FDG = [^{18}F]fluorodeoxyglucose; PET = positron emission tomography; CT = computed tomography; PR = partial response; SPD = sum of the product of the diameters; SD = stable disease; PD = progressive disease.

6.14.2 Disease progression

Only objective progressive disease (PD) according to the Cheson criteria as mentioned in Table 3 is considered in all efficacy analyses.

In particular, discontinuation due to PD (from the "End of Treatment Completion" eCRF page), without supporting objective evidence (as defined above), will not be considered as PD in the determination of best overall response rate (ORR) and in the analysis for progression-free survival (PFS).

